pregnant women receiving MRI and rTMS are unknown. Pregnant women will be excluded as per IRB policy. Female subjects are tested with a urine pregnancy test prior to every MRI session and TMS session as per IRB-approved BIAC policy. These female subjects agree not to become pregnant while remaining within the subject pool, and to notify the experimenter or subject coordinator if they become pregnant. If sexually active, the subject must agree to use appropriate contraceptive measures for the duration of the study. Medically acceptable contraceptives include: (1) surgical sterilization (such as a tubal ligation or hysterectomy), (2) approved hormonal contraceptives (such as birth control pills, patches, implants or injections), (3) barrier methods (such as a condom or diaphragm) used with a spermicide, or (4) an intrauterine device (IUD). Contraceptive measures such as Plan B (TM), sold for emergency use after unprotected sex, are not acceptable methods for routine use. If the subject has any uncertainty about whether they could be pregnant, another urine pregnancy test will be performed before they can participate in this protocol. The person(s) who will perform the urine pregnancy test will have successfully completed training as directed by the Chair of Obstetric and Gynecology of the Duke University School of Medicine. The urine pregnancy test kits used for this research study will be those commercially available test kit specified by the Chair of Obstetric and Gynecology and in routine use at DUHS.

Costs to the Subject

- Describe and justify any costs that the subject will incur as a result of participation; ordinarily, subjects should not be expected to pay for research without receiving direct benefit.

There are no costs to the subject associated with this research.

Data Analysis & Statistical Considerations

- Describe endpoints and power calculations. Provide a detailed description of how study data will be analyzed, including statistical methods used, and how ineligible subjects will be handled and which subjects will be included for analysis. Include planned sample size justification. Provide estimated time to target accrual and accrual rate. Describe interim analysis including plans to stop accrual during monitoring. Phase I studies, include dose escalation schema and criteria for dose escalation with definition of MTD and DLT.

Writer's cramp behavioral data: Endpoints: Objective handwriting parameters of duration of writing, speed of handwriting, fluency of writing movements, axial pen pressure and interpretability of handwriting will be collected using a digital tablet and a pressure sensitive pen for data analysis. Additionally, an observer blinded to subject group will complete Writer's cramp rating scale(46) and BFM Rating Scale from video recordings of subjects performing each writing task (WT-1, WT-2 and WT-3). At the initial visit, patient's medical history will be collected to evaluate appropriateness of dystonia diagnosis. Patient will also be asked about the symptoms and signs of dystonia on rating scales including Adult dystonia and disability rating scale (ADDSD)(45) Burke Fahn Marsden Rating Scale (BFM) and Pain Scale to compare their baseline symptoms before and after all 4 visits.

Sample Size justification: A review of prior research studies employing TMS in writer's cramp and healthy volunteers measuring handwriting showed statistically significant effect sizes of 15-20% on various measures of writing performance using 6-12 subjects per group(38-40,43). A power analysis of our preliminary writing behavior data from 30 subjects in visit 1 demonstrated sample size of 60 in TMS for effect size of 30% with $\alpha = 0.05$. Assuming that I will be able to achieve similar sensitivity in writing metrics, I propose to study 20 patients in TMS group using writing task and fMRI as outcome measures for analysis (visit 1). Due to the pilot nature of fMRI and TMS stimulation parameters, the minimum number of subjects needed to calculate statistical power were selected. Therefore, in order to reach pilot data set of 20 patients in TMS group with 31% screening failure rate, we need approximately 70 FHD subjects. The 70 healthy volunteers will allow us to do a better statistical power analysis of clinical and fMRI outcomes measures to evaluate effect size for TMS As a result, we would like to increase our overall goal enrollment target to 140

Our preliminary analysis of the Duke patient population reveals sufficient population of FHD subjects to recruit for our study at Duke University. Our electronic patient database identifies 186 Duke patients with a specific diagnosis of organic writer's cramp (ICD 9 code 333.84). Because ICD 10 code does not have a specific writer's cramp diagnosis, we suspect that more cases are included within the ICD G24.9 (focal dystonia) group. Therefore, the primary care providers for all 837 subjects with either of these codes may be contacted by research coordinator for patient candidacy for this research study as detailed in Section 6 eIRB submission form.

Analysis and Statistics: [name] in the Department of Neurology, **[name] and [name] in the BERD core of the Statistics Department** will be **involved** the de-identified data **analysis** but will be not involved in collecting the data. Visit 1 data of handwriting metric differences between healthy participants and focal hand dystonia patients will establish writing metric sensitivity at our site and recalculate power analysis to adjust cohort sizes, or improve technique, as indicated for visits 2, 3, and 4. For Visit **3 -5**, a two-way ANOVA will be performed with groups (healthy vs dystonia) and stimulation type (task during vs after stimulation) as the main factor within subjects. A two-way repeated measures ANOVA will be conducted with stimulation type (task during vs after stimulation) and treatment type (sham vs active) as the main factors between subjects for each handwriting measure.

fMRI data: All image pre-processing will be implemented using the FSL program (<https://wiki.biac.duke.edu/biac:fsl>). Block design fMRI data will be extracted by time-series modeling using rectangular time windows for the motor task and rest periods. Group data will then be analyzed using GLM modeling. Any fMRI network identified in writing performance from previous fMRI research using the writing task in dystonia patients will be prospectively applied to the fMRI data of the subjects. Specifically, the imaging data from the pre and post fMRI sessions will be log transformed and subtracted from each other at each site in each subject. The global mean across sites will be subtracted from each log-transformed regional value, producing regional values normalized to each subject's global mean activity. In a second normalization, the mean for each site across subjects will be subtracted from each regional value. The result of these two normalizations is a subject x region matrix with the mean activity within and across subjects removed. This will be cross-correlated with the patterns previously found in order to quantify pattern expression for individual subjects in the present group. These individual subject pattern expressions will be entered into regressions predicting brain performance in order to verify that the patterns predict performance in new group. In addition, pattern expression will be used to predict rTMS effects on writing task performance (for example, differences in RT with active and sham rTMS).

Data & Safety Monitoring

- Summarize safety concerns, and describe the methods to monitor research subjects and their data to ensure their safety, including who will monitor the data, and the frequency of such monitoring. If a data monitoring committee will be used, describe its operation, including stopping rules and frequency of review, and if it is independent of the sponsor (per 45 CFR 46.111(a) (6)).

Safety monitoring: The subjects will be fully informed of the nature of the study requirements prior to enrollment and periodically throughout the study. The subject's well being will be continuously monitored by the experimenter, and the

Principal Investigator will report all serious adverse events in an expedited manner to the Duke University Health System (DUHS) Institutional Review Board (IRB) office and all applicable regulatory authorities in accordance with the Center's standard operating procedures.

The study monitor will be [name]. [name] will ensure the quality of the study and establish that each co-investigator and research team staff is complying with the investigational plan and IRB regulations.

Monitoring of this protocol is simplified by the fact that this study involves a small number of investigators and a single facility in which the study is being conducted.

Throughout the investigation, the monitor will ensure that the facilities being used continue to be acceptable for the purposes of the study, that the investigational plan is being followed, that any changes to the protocol have received IRB

approval and accurate, complete, and current records are maintained, that accurate, complete, and timely reports are made to the IRB. This will be accomplished through quarterly meetings during which the status of the protocol,

investigators, and IRB compliance are reviewed. The monitor will review each research chart for completeness and accuracy. She will confirm that inclusion and exclusion criteria have been met for each subject enrolled, and compliance with

all other aspects of the investigational plan are met. A report will be submitted annually to the IRB. Any instances of reportable events or unanticipated problems will be reported to the Duke University IRB as outlined in the IRB Policies and

Procedures.

Data Storage and Management: Research team members are expected to follow these major principles for data storage and management.

1) All research data are stored in [name] lab folder on the Neurology server. This folder is periodically backed up onto the Dukebox research folder to generate 2 copies of all dataset with the exception of patient videos which are

maintained only on the [name] lab folder.

2) In order to give access to the 2 physicians to rate the writing assessments, deidentified patient videos are also uploaded to 2 additional secure Duke servers including DukeBox and Duke Pace environment.

3) Additionally, all data (raw and analyzed) files from [name] folder are regularly copied to a private lab database (administered by Neurology IT [name]) and accessible only to the Department Chair.

4) Study patient demographics, medical history and rating scales will also be stored in Duke Redcap database.

5) fMRI images and data will be stored on Brain Imaging and Analysis server (smb://munin3.biac.duke.edu) and data analysis performed and stored on the server.

6) Statistical tests and the statistical approach to be performed on the data must be arrived at in advance, must be appropriate and clearly stated. When feasible the approach should be arrived at in consultation with [name], **[name] and [name]**. Data dredging should be avoided by all investigators and discouraged by the PI

Research Integrity: All students, and research staff are responsible for maintaining a culture where all should feel free to voice their opinions as to the strengths and weaknesses of the research questions pursued, the methods used, and

the interpretation of results as outlined in the Department of Neurology Research SOP. Any concerns regarding data integrity should be brought immediately to the attention of the PI, Department Chair or departmental ethics ombudsman.

If for any reason, a research personnel is uncomfortable speaking with any of these individuals he/she may bring their concerns to the anonymous data integrity line in place in the Duke SoM at **[name]**

Research Responsibilities: All students, and research staff are responsible for the documentation and preservation of all data generated in the process of performing research in the [name] lab. In addition to being essential to the

generation of scientific knowledge, proper data management is a good research practice that ensures reliability and reproducibility in all our work. In addition, because the ultimate goal is for findings made in our research group to become

the basis for published scientific articles, it is of utmost importance that all source data used as the basis for any publication and materials used for grant applications to be deposited in a centralized location readily accessible to the PI and to

other members of the laboratory.

Research Training: Upon joining the [name] lab, the PI will meet individually with each student, and research staff to go over the expectations for laboratory work, including data management and research integrity in the laboratory. The

PI will go over best laboratory practices, archiving procedures, server space allocation and details of data maintenance. The PI will monitor data deposition on the servers and periodically will perform audits to ensure compliance with the established SOP. The trainee and PI will co-sign that the proper training has taken place.

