Official Title: Development of Mechanistically Informed Therapy for Task-Specific Dystonia Using Noninvasive Neuromodulation

Protocol#: Pro00094131

NCT#: NCT06422104

Document Date: 11/09/2023 (Version 1.31)

General Information

*Please enter the full title of your protocol:

Development of Mechanistically informed Therapy for Task-Specific Dystonia Using Noninvasive Neuromodulation

*Please enter the Short Title you would like to use to reference the study:

Neuromodulation Therapy for Task-Specific Dystonia

* This field allows you to enter an abbreviated version of the Study Title to quickly identify this study.

Standard Research Summary

Purpose of the Study

- Objectives & hypotheses to be tested

The overarching goal of this study is to develop a non-invasive neurostimulation therapy for patients with focal hand dystonia (FHD). Specifically, the data obtained from this study will determine if engaging the striatum during non-invasive brain stimulation in the form of Transmagnetic Stimulation (TMS) can provide prolonged improvement of dystonic symptoms. Previous work in this field has advanced our understanding of regional brain circuit disruptions in dystonia and shown some efficacy in improving focal dystonia using non-invasive brain stimulation, though as of yet the effects are relatively modest and not enduring.

Goal: To characterize baseline behavioral and structural differences between focal hand dystonia subjects and healthy volunteers and evaluate safety and feasibility of neurostimulation therapy.

Visit 1: 70 FHD subjects and 70 healthy volunteers (HV) will be recruited to provide writing samples on digital writing tablet at Duke Brain Stimulation Research Center (BSRC).

Visit 2: A small cohort of 70 FHD subjects and 70 HV from visit 1 will be recruited to undergo functional MRI brain at Duke Brain Imaging and Analysis Center (BIAC). Data from visit 2 will also be used to localize the cortical target for TMS stimulation in visits 3, 4 and 5. Overall, data from visits 1 and 2 will be used to establish baseline outcome measures for visits 3, 4 and 5.

A urine drug screen and pregnancy test prior to visits 3-5.

[figure not shown]
[figure not shown]

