TMS is a non-invasive neuromodulation strategy that has shown some benefit in WC patients. TMS involves a short intense current in a coil applied over the scalp to generate a magnetic field which then passes through the skull and induces an electric field that, depending on frequency of stimulation can depolarize or hyperpolarize local cortical neurons(24,25). A key feature of the current proposal is that I will improve upon previous applications of TMS in dystonia by targeting the deep brain region of striatum, as opposed to superficial cortex; and do so in a way that may be sufficient to induce long-term synaptic plasticity responses. I hypothesize that focal TMS stimulation designed to induce LTD in WC dystonia will improve decreased striatal activity on fMRI. To test this hypothesis, I will dose TMS using knowledge of brain circuitry in dystonia. A key parameter for effective dosing of TMS is the specific brain region to target. The striatum is a deep brain tract that is not directly targetable by TMS. However, stimulating cortical regions with TMS in a manner that affects projection neurons (as opposed to intra-cortical circuits) provides access to striatum.

Fortunately, in dystonia and WC, much work has been done to define relevant cortical inputs to striatum (25–34).

Prior research demonstrates 2 cortical regions that can be targeted by TMS to affect striatal activity in WC subjects. One potential cortical target is premotor cortex. In primates, radioactive tracer injected at premotor and motor cortex demonstrated direct projection of premotor cortical axons to striatum, particularly putamen(35,36). Studies in WC using *in vivo* tract tracing suggest the premotor to putamen pathway is impaired(37).

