 3. Healthy volunteers will undergo TMS stimulation protocol development. Subjects will receive 10Hz active stimulation at premotor cortex during one visit and primary sensory cortex during another visit for up to 20 minutes with stimulation intensity up to 120% of resting motor threshold which is within the published safety guidelines (47) and based on previously published protocol used in multiple human studies(13–16). The resting motor threshold is a baseline stimulation intensity determined using the protocol in step 2. Additional stimulation parameters including duration of continuous stimulation, interstimulus interval, stimulation intensity, orientation of magnetic coil, biphasic or monophasic stimulation will be developed with healthy volunteers based on the published safety guidelines(47), writing assessment (includes writing and non-writing sampling) and feasibility within 20 minutes stimulation paradigm.
 4. WC subjects will undergo TMS stimulation visits 3, 4 and 5. 2 visits will include active TMS stimulation while the remaining one visit will be a control sham stimulation. Of the 2 active TMS stimulation visits, subjects will receive TMS at premotor cortex during one visit and at primary sensory cortex during the other active TMS visit. The dosage of active stimulation will be 10Hz for up to 20 minutes with resting motor threshold up to 120% which is within the published safety guidelines (47) and based on previously published protocol used in multiple human studies(13–16). During both active and sham stimulation blocks, subjects will be asked to perform a writing task of writing a diverse paragraph as an online stimulation task. The stimulation block will be preceded and followed by a writing assessment and TMS acute side effects survey to assess safety of the stimulation. Visit 3, 4, and 5 will occur 1 week apart. Subject will undergo fMRI after each of the 3 TMS visits.

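### The plan asks whether engaging the striatum helps, but it specifies no putamen analysis, and active versus sham cannot separate a striatal effect from a local cortical one

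*Combined protocol and SAP*

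**What the plan says.** The striatal question appears three times.

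- Purpose of the Study: the data "will determine if engaging the striatum during non-invasive brain stimulation" with TMS can bring lasting relief of dystonia.
- Background & Significance: "I hypothesize that focal TMS stimulation designed to induce LTD in WC dystonia will improve decreased striatal activity on fMRI". The proposal is also said to "improve upon previous applications of TMS in dystonia by targeting the deep brain region of striatum, as opposed to superficial cortex".
- End of Background & Significance: stimulating two sites on separate visits is meant to show which is the better target for changing putamen activity.

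The design is in Design & Procedures, Visits 3, 4 and 5, step 4. For patients, "2 visits will include active TMS stimulation while the remaining one visit will be a control sham stimulation", and "subjects will receive TMS at premotor cortex during one visit and at primary sensory cortex during the other active TMS visit". An fMRI scan follows each of the three visits. Background & Significance explains that both sites were selected because stimulating them can influence the striatum.

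The analysis is in Data Analysis & Statistical Considerations. Under Analysis and Statistics there are two ANOVAs: one on group and task timing, the other on task timing and sham versus active for each handwriting measure. Neither has a term for stimulation site or for imaging. Under fMRI data, pre/post log differences are normalised twice and scored against writing-network patterns from earlier research, and "pattern expression will be used to predict rTMS effects on writing task performance". The words putamen and striatum do not occur in that paragraph.

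The Purpose section also gives a narrower goal: to describe baseline differences and "evaluate safety and feasibility of neurostimulation therapy".

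**The concern.** A trial that sets out to determine whether engaging a deep structure helps needs one of two things. It could have a comparison condition that stimulates cortex without engaging that structure, or it could have a specified measurement of the structure tied to outcome. This plan has neither. The three conditions differ in whether cortex is stimulated and where, and both active sites are presumed to reach the striatum.

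Two readings of the results would stay open. If writing improves under active TMS, local stimulation of premotor or sensory cortex could account for it as well as the putamen could. If writing does not improve, the specified analyses do not tell a putamen that was not engaged from one that was engaged without benefit. The aim of choosing the better site for acting on the putamen has no matching test at all. Meanwhile the scans that could inform all of this are already scheduled.

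**Working it through.** The plan gives no figure for this question to reproduce. Its power calculation concerns handwriting. The check is therefore of what each stated analysis can identify.

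**1. Active versus sham.** For illustration, let the benefit at site k be L_k + S_k, where L is the local cortical part and S the part passing through the striatum, with both zero under sham.

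- Active minus sham at site k estimates L_k + S_k.
- Premotor minus sensory estimates (L_p − L_s) + (S_p − S_s).

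Neither contrast isolates S.

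A simulation shows the same thing: 20,000 trials, n = 20, one active-minus-sham difference per patient, two-sided 0.05. The standardised effect d is assumed. In the striatal scenario, benefit correlates with putamen change at an assumed r = 0.6; in the cortical-only scenario it does not.

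| d | Active vs sham significant: striatal | Active vs sham significant: cortical only | Putamen–benefit correlation significant: striatal | Putamen–benefit correlation significant: cortical only |
|---|---|---|---|---|
| 0.5 | 56% | 57% | 84% | 5% |
| 0.66 | 80% | 80% | 84% | 5% |
| 0.8 | 92% | 93% | 84% | 5% |

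The sham contrast is equally likely to be positive under either mechanism. A putamen–benefit correlation does separate these two scenarios, but the plan does not contain one.

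**2. The network analysis.** This is a real brain–behaviour link, since pattern expression is used to predict the TMS effect. It is not a putamen test. The network's regions are not listed, no putamen value enters the regression, and the example outcome (RT) is not among the handwriting parameters listed as endpoints.

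**3. The two normalisations.** Let x_ij be the log change for patient i at region j.

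- Subtracting the patient's global mean gives x_ij − x̄_i.
- Subtracting the mean of those values across patients at region j gives u_ij = (x_ij − x̄_i) − (x̄_j − x̄).
- The average of u_ij over patients is then zero for every region, the putamen included.

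If this is done separately for each condition, the average putamen change is zero by construction, and the striatal hypothesis cannot be tested from that matrix. If conditions are pooled first, only the overall mean is removed and differences between conditions survive. The text does not say which applies. Differences between patients survive in both cases, so a regression across patients remains possible.

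**4. What an added regression could deliver at n = 20** (two-sided 0.05, one difference per patient).

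- Smallest significant correlation: t / √(t² + 18) with t(0.975, 18) = 2.101 gives 2.101 / √22.41 = 0.444.
- Correlation with 80% power, by Fisher z: tanh[(1.96 + 0.842) / √17] = tanh(0.680) = 0.59.
- Power at an assumed r is Φ(atanh(r)·√17 − 1.96). The N for 80% power is [(1.96 + 0.842) / atanh(r)]² + 3, rounded up.

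| Assumed r | Power at n = 20 | N for 80% power |
|---|---|---|
| 0.3 | 25% | 85 |
| 0.4 | 42% | 47 |
| 0.5 | 62% | 30 |
| 0.6 | 82% | 20 |

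An observed r of 0.4 would have a 95% interval of about −0.05 to 0.72.

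**The case against.** The best defence is that this is a pilot. The stated goal is baseline description, safety and feasibility. Step 6 of the visit 3–5 procedures confines those data to safety of the stimulation protocol and feasibility of the writing task and fMRI. The sample size text calls the TMS group a pilot data set. On that view the fault is one over-ambitious sentence. This bears on how serious the point is, but it does not withdraw the sentence, the striatal hypothesis or the putamen aim.

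It can also be said that the fMRI section includes a group GLM and a matrix of regional values, so putamen results could be extracted. They could, but no contrast, region or link to benefit is stated.

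A reader might go further than the documents allow in four ways.

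- *That a positive trial would show only that cortical TMS beats sham.* This overlooks the network regression, which could also show that benefit tracks a writing network.
- *That the plan would credit the striatum with any benefit, or that it promises a superficial-cortex comparator.* No attribution rule is stated, and the remark about superficial cortex contrasts this proposal with earlier TMS studies, not with an arm of this one.
- *That the putamen's share of the network score can be estimated.* The number of regions and their weights are not given. Under equal weights over the same regions, the score is zero for every patient once the global mean is removed.
- *That a significant putamen contrast together with a significant regression would justify attribution to the striatum.* The scans record writing-task activity after stimulation. If a purely cortical effect improved writing, putamen activity could change as a result, and both tests could be positive.

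**Conclusion.** The point stands as a gap between question and analysis. Followed exactly, the plan cannot attribute benefit to striatal engagement, because sham is the only control and both active sites are presumed to reach the striatum. Nor does it test its own putamen hypothesis or its site-selection aim, because no putamen measure is specified and the double normalisation may remove the average change.

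This is more than missing detail, but it is a cheap improvement to a pilot and does not invalidate the active-versus-sham comparison. The conclusion about what the contrasts identify needs no numerical assumption. The simulation and power figures rest on assumed effects and correlations, since the documents give none. Even with the added analysis, 20 patients allow only exploratory, correlational evidence, with 80% power at a true r of about 0.59 and 42% at 0.4.

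**What to change.** In the fMRI data paragraph, add two analyses.

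1. A prespecified putamen region of interest, with within-patient contrasts of writing-task activity: premotor minus sham, sensory minus sham, and premotor versus sensory for the site-selection aim. Compute these before the across-subject mean is removed, and say whether the normalisation is done by condition or on pooled conditions.
2. An exploratory regression of the active-minus-sham handwriting change on the matching putamen difference. Run it by site, or in one mixed model with a patient effect, because each patient contributes two differences that share one sham visit. Report estimates with confidence intervals beside the network-pattern regression, and do not use the result as a pass/fail rule for attribution.

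In Purpose of the Study, restate the objective along these lines: active versus sham tests the effect of cortical TMS on writing; striatal involvement is examined through putamen activity as exploratory, correlational evidence in 20 patients.

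The cost is one region-of-interest analysis and some rewording. No arm, scan or patient is added. The downside is a little more analysis and a weaker mechanistic claim. Settling this before the data are analysed also meets the plan's own requirement, under Data & Safety Monitoring, that the statistical approach be fixed beforehand.
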